9.2.2. Exclusion Criteria

There are no exclusion criteria for this study.

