9.3.2. Endpoints

The BSRBR-RA is an existing, efficient data collection system for evaluating a range of safety outcomes associated with therapies used to treat RA including cancers,^{11,18} cardiovascular events¹⁹ and serious infections.¹⁷ The endpoints collected in BSRBR-RA are events associated with RA itself and therapies used to treat moderate to severe disease. The following events of interest have been pre specified for this study.

1. Hospitalised infections overall.
2. NMSC.
3. Cardiac disorders: including but not limited to heart failure, coronary artery disease, myocardial infarction, and other cardiac disorders.
4. Malignancies, excluding NMSC.
5. Events associated with use during pregnancy.

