9.7. Data Analysis

All statistical analyses will be performed by BSRBR using Stata. The annual analyses will include all patients who have received Ruxience (baseline characteristics) and event incidence reports will include all patients with study follow-up data.

Analyses will be undertaken at 12 monthly intervals and will include recruitment details, baseline characteristics and crude event rates.

The final analysis will provide the incidence rates of safety events of interest overall. If sample size allows, additional analysis in subgroups by gender and new users versus switcher from originator will be undertaken.

The general analytic approach will be descriptive and include rates of events of interest among Ruxience-treated patients. Data will be presented as number of events, incidence rates and 95 % confidence intervals. Such analyses will be performed by and at the direction of BSRBR based on an a priori statistical analysis plan (SAP) maintained by University of Manchester and shared with the Sponsor. The codes will be harmonised with other registers conducting similar analysis. A draft set of MedDRA codes is included in:

Index Date

The Index Date is the date of Ruxience initiation. Patients who switch from another therapy to Ruxience while they are enrolled in BSRBR-RA are eligible for enrollment, and the index date will be the date of Ruxience initiation.

Risk Window

Patients will be evaluated for safety events of interest while exposed to Ruxience and accrue person-time from Index Date until the first occurrence of the event of interest, death, date of last scheduled clinical data provision to the register, lost to follow up, exit from the register or completion of 3 years of follow up. The final report will censor all patients at 3 years after Date of Study Start. Follow up will be uniquely determined for each safety endpoint of interest.

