			10008089 Cerebral artery occlusion; 10008092 Cerebral artery thrombosis; 10008111 Cerebral haemorrhage; 10008118 Cerebral infarction; 10008132 Cerebral thrombosis; 10018985 Haemorrhage intracranial; 10022758 Intracranial aneurysm; 10022840 Intraventricular haemorrhage; 10022841 Intraventricular haemorrhage neonatal; 10024119 Left ventricular failure; 10024242 Leriche syndrome; 10034476 Pericardial haemorrhage; 10036511 Precerebral artery occlusion; 10039163 Right ventricular failure; 10039330 Ruptured cerebral aneurysm; 10042316 Subarachnoid haemorrhage; 10042434 Sudden death; 10047279 Ventricle rupture; 10048380 Aneurysm ruptured; 10048761 Atrial rupture; 10049418 Sudden cardiac death; 10049993 Cardiac death; 10050403 Carotid artery dissection; 10051093 Cardiopulmonary failure; 10051328 Carotid aneurysm rupture; 10052019 Femoral artery occlusion; 10053633 Cerebellar artery occlusion; 10053649 Vascular rupture; 10053949 Vascular pseudoaneurysm ruptured; 10055803 Haemorrhage coronary artery; 10058178 Aortic occlusion; 10060874 Aortic rupture; 10060953 Ventricular failure; 10060964 Arterial haemorrhage; 10062585 Peripheral arterial occlusive disease; 10062599 Arterial occlusive disease; 10063081 Acute left ventricular failure; 10063082 Acute right ventricular failure ; 10063083 Chronic left ventricular failure; 10063084 Chronic right ventricular failure; 10064595 Haemorrhagic arteriovenous malformation; 10064601 Iliac artery occlusion; 10065441 Venous haemorrhage; 10065558 Aortic

090177e1953dcb50\Approved\Approved On: 16-Oct-2020 13:28 (GMT)

Table 2. ICD and MedDRA Codes for Select Safety Endpoints

Event	ARTIS		BIOBADASER, BSRBR, RABBIT
	Operationalisation	Validation ICD	Operationalisation (Final list TBD based on reported endpoints)
			arteriosclerosis; 10067057 Basal ganglia haemorrhage; 10067116 Carotid arteriosclerosis; 10068119 Aortic dissection rupture; 10068119 Aortic dissection rupture; 10068230 Cardiorenal syndrome; 10069694 Brachiocephalic artery occlusion; 10069695 Subclavian artery occlusion; 10069696 Coeliac artery occlusion; 10071716 Vertebral artery dissection; 10072043 Central nervous system haemorrhage; 10072789 Iliac artery rupture; 10073565 Intracranial artery dissection; 10073565 Intracranial artery dissection; 10073681 Epidural haemorrhage; 10075449 Brachiocephalic arteriosclerosis; 10076203 Radiation associated cardiac failure.

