NMSC	Identified through the Cancer register as all malignancies with ICD-O/2 code C44, and all basal cell cancers recoded in the register's subcomponent on basal cell cancers Alt: all invasive NMSC, identified as non-benign ICD-O/2 code C44, and no basal cell cancers.	About 99% of cancers have been morphologically verified. Reporting of incident cancers (including invasive malignancies as well as cancer in situ) is mandatory and semi automated, resulting in an estimated coverage greater than 95%.	10004146 Basal cell carcinoma; 10004178 Basosquamous carcinoma; 10004179 Basosquamous carcinoma of skin; 10006059 Bowen's disease; 10007390 Carcinoma in situ of skin; 10064055 Lip squamous cell carcinoma; 10063693 Malignant neoplasm of eyelid; 10040808 Skin cancer; 10055115 Skin cancer metastatic 10041834 Squamous cell carcinoma of skin.
Malignancy	All invasive malignancies recorded in the cancer register, excluding NMSC.	See NMSC.	Malignant or unspecified tumours (SMQ).

090177e1953dcb50\Approved\Approved On: 16-Oct-2020 13:28 (GMT)

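### The malignancy code rule for this register conflicts with endpoint 4: it does not exclude NMSC and it admits unspecified tumours, so it can overstate the malignancy rate

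*Protocol*

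**What the plan says.** Section 9.3.2 lists NMSC as endpoint 2 and "Malignancies, excluding NMSC" as endpoint 4. Table 1 in section 9.5 also has separate rows for the two.

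Annex 1 Table 2 gives the operational definitions. In the malignancy row:
- The ARTIS cell reads "All invasive malignancies recorded in the cancer register, excluding NMSC".
- The cell for BIOBADASER, BSRBR and RABBIT reads "Malignant or unspecified tumours (SMQ") and nothing more.

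The NMSC row directly above, in the same column, is a list of MedDRA terms that includes "10063693 Malignant neoplasm of eyelid; 10040808 Skin cancer; 10055115 Skin cancer metastatic".

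The list is not final. The column is headed "Operationalisation (Final list TBD based on reported endpoints"), and section 9.7 says "A draft set of MedDRA codes is included in" the annex and "The codes will be harmonised with other registers conducting similar analysis".

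On counting, section 9.7 follows patients for NMSC and other malignancies from drug initiation to the first event, loss to follow-up or three years. Section 9.2.2 states "There are no exclusion criteria for this study". No section says how a cancer diagnosed before the Index Date is to be handled.

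**The concern.** The endpoint and its code rule describe different sets of events. The exclusion of NMSC was written into Table 2 for ARTIS but not for the register that supplies this study's data. By its name the SMQ also takes in tumours whose malignancy is not established, which neither endpoint 4 nor the ARTIS cell does.

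Malignancy is an important potential risk in the RMP. Incidence rates are the study's only result and there is no comparator, so an error in the case definition passes straight into the reported figure. Three effects follow if the cell is applied as it stands:
- a skin carcinoma can appear under endpoints 2 and 4;
- an unspecified tumour can be reported as a malignancy;
- either event closes endpoint-4 follow-up, so a later true malignancy in that patient is no longer observed for this endpoint.

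A secondary gap is that, with first-event counting and no rule on prior cancer, a recurrence of a pre-index cancer could be taken as incident.

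**Working it through.** **1. The definitions side by side.**
- Section 9.3.2, endpoint 4: malignancy, NMSC out.
- Table 1: malignancy, NMSC out.
- Table 2, ARTIS: invasive malignancy, NMSC out.
- Table 2, BSRBR column: the SMQ, with no NMSC exclusion and unspecified tumours in.

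Three agree on NMSC and the one that governs this study's data does not. The contents of the SMQ are not in the protocol. That it reaches NMSC is inferred from its name and from NMSC terms that are malignant by name, such as skin cancer and malignant neoplasm of eyelid.

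**2. The plan's own figures.** Table 1 reproduces with exact (Clopper-Pearson) limits: lower = Beta(0.025; x, n−x+1), upper = Beta(0.975; x+1, n−x), and for x = 0 upper = 1 − 0.025^(1/n).
- Malignancy excluding NMSC: 1/73 = 0.0137 (0.0003 to 0.0740). The protocol gives 0.014 (0.000 to 0.074).
- NMSC: 0/73 = 0 (0 to 0.0493). The protocol gives 0.000 (0.000 to 0.049).

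All six rows agree to three decimals.

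**3. Direction.** Assume the SMQ covers all endpoint-4 malignancies. A patient's first counted event under the literal rule then falls at the earlier of the first target and the first non-target event, so never later than under endpoint 4. The number of patients with an event can only stay the same or rise, and person-time can only stay the same or fall. This component of the rate is therefore equal or higher, never lower.

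**4. Size.** Let r be the rate of non-target events (NMSC plus unspecified tumours) divided by the rate of endpoint-4 events. With constant hazards, counted rate / target rate = 1 + r. The protocol gives no r. Assumed values of 0, 0.1, 0.25, 0.5 and 1 give factors of 1.0, 1.1, 1.25, 1.5 and 2.0.

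At the scale of Table 1:
- adding its own NMSC count (0) leaves 1/73 = 0.0137;
- one non-target tumour gives 2/73 = 0.0274 (0.0033 to 0.0955);
- two give 3/73 = 0.0411 (0.0086 to 0.1154).

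The 73 are the RMP population, not the expected size of this cohort, so these are illustrations.

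**5. Prior cancer.** Let q be the share of patients with prior cancer and m their rate of counted events relative to the rest. Then whole-cohort rate / cancer-naive rate = 1 − q + q·m. Neither is given. Assuming q = 0.05 to 0.20 and m = 0.8 to 3:
- lowest: 1 − 0.20 + 0.20 × 0.8 = 0.96;
- highest: 1 − 0.20 + 0.20 × 3 = 1.40;
- at m = 1 the ratio is 1.0 for any q.

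The direction is not fixed.

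**The case against.** The strongest reply is that nothing is settled. The column is labelled as awaiting a final list, section 9.7 calls the codes a draft, and an SAP not available here will govern the analysis. The endpoint itself excludes NMSC and the list to subtract sits one row above. This stands in part: it would be wrong to infer that the sponsor has decided to count NMSC. It does not remove the conflict. The ENCePP checklist (item 6.2) points to this annex as the place where outcomes are defined, and the column heading ties the final list to what is reported, which fits poorly with an a priori analysis plan.

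A second reply is that cases are checked. Section 9.4 describes linkage to the cancer register, section 9.8 nurse review and hospital validation of patient-reported serious events, and section 12 bases the final report on linked data. That is fair, and it means that unconfirmed tumours need not go unchecked. Still, the cell does not make confirmation a condition for counting, and validating a skin carcinoma does not move it out of endpoint 4.

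A third concerns comparability. BIOBADASER and RABBIT share this cell, so a reader who infers that BSRBR would be out of line with the other registers goes too far. The mismatch is with ARTIS only.

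A fourth concerns prior cancer. A reader might infer that having no exclusion criteria inflates the rate. The documents do not support this: the target population is all Ruxience initiators, patients with prior cancer contribute person-time, and a new primary cancer in them is a genuine incident event. Inflation needs recurrence or progression to be counted, which the protocol neither states nor rules out.

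**Conclusion.** The contradiction is in the text and should be resolved before the code list is finalised. Applied as written, the BSRBR cell counts a wider set of events than endpoint 4 and stops follow-up at events outside it, so it can overstate the malignancy rate. This rests on reading the SMQ's scope from its name and on such events occurring.

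It is tempting to say that the rate is overstated, or by how much. Neither is supported. The factor is 1 + r with r unknown, and Table 1 records no NMSC among 73 patients. Late cancer registration (section 9.4) and events unknown to the rheumatology team (section 9.9) act downward, so the net bias is not established. Those are separate errors, however, and do not correct a wrong case definition. The doubling from 1/73 to 2/73 shows how sensitive a small count is; it is not an estimate of the bias.

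Prior cancer is a secondary point about an unstated rule, with no fixed direction.

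**What to change.** In Annex 1 Table 2:
- define the malignancy cell as the SMQ minus the NMSC terms listed in the row above;
- count only malignant tumours in the main rate, using the cancer-register linkage or hospital validation already in place;
- report tumours of unspecified malignancy on a separate line;
- make the same edit for BIOBADASER and RABBIT, so that the registers sharing the column stay aligned with each other and move closer to ARTIS.

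In section 9.7, state that recurrence or progression of a cancer diagnosed before the Index Date is not an incident event. Keep patients with prior malignancy in the cohort and, where numbers allow, show them as a separate stratum. Baseline comorbidity (section 9.3.1) and the cancer-register linkage are the sources for identifying them.

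The cost is a code-list edit, one sentence on prior cancer and possibly one extra stratum. Slightly fewer events may be counted. Some NMSC terms are general, skin cancer for example, so a case coded only that way should be checked against the cancer register before it is removed from endpoint 4.

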ANNEX 2. ENCePP CHECKLIST FOR STUDY PROTOCOLS

EUROPEAN MEDICINES AGENCY
 SCIENCE MEDICINES HEALTH

bDoc.Ref. EMA/540136/2009

European Network of Centres for
 Pharmacoepidemiology and
 Pharmacovigilance

ENCePP Checklist for Study Protocols (Revision 4)

Adopted by the ENCePP Steering Group on 15/10/2018

The [European Network of Centres for Pharmacoepidemiology and Pharmacovigilance \(ENCePP\)](#) welcomes innovative designs and new methods of research. This Checklist has been developed by ENCePP to stimulate consideration of important principles when designing and writing a pharmacoepidemiological or pharmacovigilance study protocol. The Checklist is intended to promote the quality of such studies, not their uniformity. The user is also referred to the [ENCePP Guide on Methodological Standards in Pharmacoepidemiology](#), which reviews and gives direct electronic access to guidance for research in pharmacoepidemiology and pharmacovigilance.

For each question of the Checklist, the investigator should indicate whether or not it has been addressed in the study protocol. If the answer is "Yes", the section number of the protocol where this issue has been discussed should be specified. It is possible that some questions do not apply to a particular study (for example, in the case of an innovative study design). In this case, the answer 'N/A' (Not Applicable) can be checked and the "Comments" field included for each section should be used to explain why. The "Comments" field can also be used to elaborate on a "No" answer.

This Checklist should be included as an Annex by marketing authorisation holders when submitting the protocol of a non-interventional post-authorisation safety study (PASS) to a regulatory authority (see the [Guidance on the format and content of the protocol of non-interventional post-authorisation safety studies](#)). The Checklist is a supporting document and does not replace the format of the protocol for PASS presented in the Guidance and Module VIII of the Good pharmacovigilance practices (GVP).

Study title: An Active Surveillance, Post Authorization Safety Study (PASS) of Serious Infection, Malignancy, Cardiovascular (CV) and Other Safety Events of Interest among Patients Treated with Ruxience for Moderately to Severely Active Rheumatoid Arthritis (RA) within the British Society for Rheumatology Biologics Register Rheumatoid Arthritis (BSRBR RA).

EU PAS Register® number:
Study reference number (if applicable):B3281011

Section 1: Milestones		Yes	No	N/A	Section Number
1.1	Does the protocol specify timelines for				
	1.1.1 Start of data collection ¹				6
	1.1.2 End of data collection ²				6
	1.1.3 Progress report(s)				N/A
	1.1.4 Interim report(s)				6
	1.1.5 Registration in the EU PAS Register®				6

¹ Date from which information on the first study is first recorded in the study dataset or, in the case of secondary use of data, the date from which data extraction starts.

² Date from which the analytical dataset is completely available.

090177e1953dcb50Approved\Approved On: 16-Oct-2020 13:28 (GMT)

PFIZER CONFIDENTIAL

CT24-WI-GL02-RF02 2.0 Non-Interventional Study Protocol Template For Secondary Data Collection Study

01-Jun-2020

Page 28 of 34

Section 1: Milestones	Yes	No	N/A	Section Number
1.1.6 Final report of study results.				6

Comments:

Section 2: Research question	Yes	No	N/A	Section Number
2.1 Does the formulation of the research question and objectives clearly explain:				8
2.1.1 Why the study is conducted? (e.g. to address an important public health concern, a risk identified in the risk management plan, an emerging safety issue)				7
2.1.2 The objective(s) of the study?				8
2.1.3 The target population? (i.e. population or subgroup to whom the study results are intended to be generalised)				8
2.1.4 Which hypothesis(-es) is (are) to be tested?				N/A
2.1.5 If applicable, that there is no a priori hypothesis?				9.7

Comments:

Section 3: Study design	Yes	No	N/A	Section Number
3.1 Is the study design described? (e.g. cohort, case-control, cross-sectional, other design)				8, 9.1
3.2 Does the protocol specify whether the study is based on primary, secondary or combined data collection?				9.1
3.3 Does the protocol specify measures of occurrence? (e.g., rate, risk, prevalence)				8
3.4 Does the protocol specify measure(s) of association? (e.g. risk, odds ratio, excess risk, rate ratio, hazard ratio, risk/rate difference, number needed to harm (NNH))				N/A
3.5 Does the protocol describe the approach for the collection and reporting of adverse events/adverse reactions? (e.g. adverse events that will not be collected in case of primary data collection)				N/A

Comments:

Section 4: Source and study populations	Yes	No	N/A	Section Number
4.1 Is the source population described?				9.2
4.2 Is the planned study population defined in terms of:				
4.2.1 Study time period				9.4
4.2.2 Age and sex				N/A

Section 4: Source and study populations	Yes	No	N/A	Section Number
4.2.3 Country of origin				9.2
4.2.4 Disease/indication				9.2
4.2.5 Duration of follow-up				9.4
4.3 Does the protocol define how the study population will be sampled from the source population? (e.g. event or inclusion/exclusion criteria)				9.2

Comments:

--

Section 5: Exposure definition and measurement	Yes	No	N/A	Section Number
5.1 Does the protocol describe how the study exposure is defined and measured? (e.g. operational details for defining and categorising exposure, measurement of dose and duration of drug exposure)				9.2.1-9.6
5.2 Does the protocol address the validity of the exposure measurement? (e.g. precision, accuracy, use of validation sub-study)				9.2.1-9.6
5.3 Is exposure categorised according to time windows?				9.2.1-9.6
5.4 Is intensity of exposure addressed? (e.g. dose, duration)				9.2.1-9.6
5.5 Is exposure categorised based on biological mechanism of action and taking into account the pharmacokinetics and pharmacodynamics of the drug?				9.2.1-9.6
5.6 Is (are) (an) appropriate comparator(s) identified?				N/A

Comments:

--

Section 6: Outcome definition and measurement	Yes	No	N/A	Section Number
6.1 Does the protocol specify the primary and secondary (if applicable) outcome(s) to be investigated?				9.5.2
6.2 Does the protocol describe how the outcomes are defined and measured?				Appendix 1
6.3 Does the protocol address the validity of outcome measurement? (e.g. precision, accuracy, sensitivity, specificity, positive predictive value, use of validation sub-study)				N/A
6.4 Does the protocol describe specific outcomes relevant for Health Technology Assessment? (e.g. HRQoL, QALYs, DALYS, health care services utilisation, burden of disease or treatment, compliance, disease management)				N/A

Comments:

--

Section 7: Bias	Yes	No	N/A	Section Number
7.1 Does the protocol address ways to measure confounding? (e.g. confounding by indication)				N/A
7.2 Does the protocol address selection bias? (e.g. healthy user/adherer bias)				N/A
7.3 Does the protocol address information bias? (e.g. misclassification of exposure and outcomes, time-related bias)				N/A

Comments:

--

Section 8: Effect measure modification	Yes	No	N/A	Section Number
8.1 Does the protocol address effect modifiers? (e.g. collection of data on known effect modifiers, sub-group analyses, anticipated direction of effect)				N/A

Comments:

--

Section 9: Data sources	Yes	No	N/A	Section Number
9.1 Does the protocol describe the data source(s) used in the study for the ascertainment of:				
9.1.1 Exposure? (e.g. pharmacy dispensing, general practice prescribing, claims data, self-report, face-to-face interview)				N/A
9.1.2 Outcomes? (e.g. clinical records, laboratory markers or values, claims data, self-report, patient interview including scales and questionnaires, vital statistics)				9.6
9.1.3 Covariates and other characteristics?				9.6
9.2 Does the protocol describe the information available from the data source(s) on:				
9.2.1 Exposure? (e.g. date of dispensing, drug quantity, dose, number of days of supply prescription, daily dosage, prescriber)				9.6
9.2.2 Outcomes? (e.g. date of occurrence, multiple event, severity measures related to event)				9.6
9.2.3 Covariates and other characteristics? (e.g. age, sex, clinical and drug use history, co-morbidity, co-medications, lifestyle)				9.6
9.3 Is a coding system described for:				
9.3.1 Exposure? (e.g. WHO Drug Dictionary, Anatomical Therapeutic Chemical (ATC) Classification System)				N/A
9.3.2 Outcomes? (e.g. International Classification of Diseases (ICD), Medical Dictionary for Regulatory Activities (MedDRA))				9.5.2 and Appendix 1
9.3.3 Covariates and other characteristics?				9.6
9.4 Is a linkage method between data sources described? (e.g. based on a unique identifier or other)				N/A

Comments:

Section 10: Analysis plan	Yes	No	N/A	Section Number
10.1 Are the statistical methods and the reason for their choice described?				9.9
10.2 Is study size and/or statistical precision estimated?				N/A
10.3 Are descriptive analyses included?				
10.4 Are stratified analyses included?				N/A
10.5 Does the plan describe methods for analytic control of confounding?				N/A
10.6 Does the plan describe methods for analytic control of outcome misclassification?				N/A
10.7 Does the plan describe methods for handling missing data?				N/A
10.8 Are relevant sensitivity analyses described?				N/A

Comments:

Section 11: Data management and quality control	Yes	No	N/A	Section Number
11.1 Does the protocol provide information on data storage? (e.g. software and IT environment, database maintenance and anti-fraud protection, archiving)				9.8
11.2 Are methods of quality assurance described?				9.10
11.3 Is there a system in place for independent review of study results?				

Comments:

Section 12: Limitations	Yes	No	N/A	Section Number
12.1 Does the protocol discuss the impact on the study results of:				
12.1.1 Selection bias?				N/A
12.1.2 Information bias?				9.11
12.1.3 Residual/unmeasured confounding? (e.g. anticipated direction and magnitude of such biases, validation sub-study, use of validation and external data, analytical methods).				N/A
12.2 Does the protocol discuss study feasibility? (e.g. study size, anticipated exposure uptake, duration of follow-up in a cohort study, patient recruitment, precision of the estimates)				N/A

Comments:

Section 13: Ethical/data protection issues	Yes	No	N/A	Section Number
13.1 Have requirements of Ethics Committee/ Institutional Review Board been described?				10.4
13.2 Has any outcome of an ethical review procedure been addressed?				10.4
13.3 Have data protection requirements been described?				10.1

Comments:

Section 14: Amendments and deviations	Yes	No	N/A	Section Number
14.1 Does the protocol include a section to document amendments and deviations?				5

Comments:

Section 15: Plans for communication of study results	Yes	No	N/A	Section Number
15.1 Are plans described for communicating study results (e.g. to regulatory authorities)?				12
15.2 Are plans described for disseminating study results externally, including publication?				12

Comments:

Name of the main author of the protocol: [name]

Date: 25 Sept 2020

Signature: _____

